#### 5.2. Analysis methods

*Main statistical analyses.* The main statistical analysis is planned after the last patient has fulfilled the pre-defined follow-up period. PFS will be calculated from the day of randomization to first recorded disease progression according to RECIST v1.1 or when applicable iRECIST, or death. Patients who have not had disease progression at the time of final analysis will be censored at the date last known to be alive and progression-free. The analyses will compare the treatment groups in total as well as groups stratified by primary tumor sidedness and (K)RAS/BRAF mutation status.

*Interim analyses.* Interim analyses will apply to data on safety, tolerability, possible detrimental effects, and curative outcomes, and will be based on purely clinical judgment by the External Data and Safety Monitoring Committee. These types of data will be reported as the number of events.

*Descriptive statistics.* Demographic and clinical characteristics will be presented as means and standard deviations, medians with minimum and maximum values, or frequencies and percentages, as appropriate. Further statistical analyses will be separated to primary analyses, including only comparison of primary end point between two treatment arms, and secondary analyses, including stratified analyses on primary and secondary end points as well as number of analyses on secondary end points.

*Primary analysis.* Median PFS time will be compared between study arms by drawing Kaplan-Meier survival curves and performing log-rank test. HR with the corresponding 95% CI and p-values will be estimated by Cox proportional hazards model.

*Secondary analyses.* Distribution of PFS times stratified by the primary tumor sidedness and (K)RAS/BRAF mutation status will be illustrated graphically by Kaplan-Meier curves and compared by log-rank test. To assess the hazard rates for disease progression within each strata, Cox proportional hazards model will be estimated and, if appropriate, adjusted for relevant covariates. The results will be presented as HR with the corresponding 95% CI and p-values.

Safety. The number of serious adverse events (SAE) will be summarized and presented by trial arm. In addition, information will be given on the number of SAE per participant, together with details on the causality, expectedness, and outcome of each SAE experienced. Summaries of suspected unexpected serious adverse reaction (SUSAR) events will also be presented by trial arm.

Tolerability. Summaries by trial arm will be produced to show the proportion of participants experiencing each grade of CTCAE toxicities overall and during each treatment cycle. For more detailed summaries, this information will also be broken down into the different types of toxicities.

QoL. This will be summarized for each treatment arm at study enrolment, completion of the active therapy of the first treatment sequence (after 16 weeks), and disease progression, using the consensus modules EORTC QLQ-C30, EORTC QLQ-CIPN20, and EQ-5D-5L. The data will be illustrated graphically and presented as mean scores with 95% CI at separate time points. The differences in QoL between two treatment arms throughout the study period will be assessed by estimating a linear mixed model with fixed effects for time and treatment arm and the interaction between these two. Random effects for patients will be included. A significant interaction will quantify differences between the groups and serve as an omnibus test.

Safety and tolerability in the treatment arms will be compared by  $\chi^2$  or Fisher's exact test, as appropriate.

ORR is defined as the percentage of patients with a confirmed CR or PR. The proportion of participants achieving at least PR will be summarized with corresponding 95% CI for each treatment arm. The difference between the trial arms in the proportion of participants achieving at least PR will also be presented with corresponding 95% CI. The difference between participants achieving at least PR and remaining participants will be assessed using logistic regression adjusting for treatment group and stratification factors. Odds ratios with corresponding 95% CI and p-values will be presented for all variables incorporated in the model.

SSCRR is defined as the percentage of patients with a confirmed resection of metastatic disease with microscopically free margin (R0). Corresponding analyses as those to be performed for ORR will be applied for SSCRR.

DOR is defined as the time from the first documentation of CR/iCR or PR/iPR to disease progression. DOR Kaplan-Meier curves will be drawn and compared by log-rank test. The median DOR with corresponding 95% CI will be presented by treatment group. Stratified analyses will be performed as well. The Cox proportional hazards model, adjusting for the stratification factors, will also be used to compare DOR

between the treatment groups. HR, 95%CI and p-values will be presented for all variables incorporated in the model.

OS is defined as the time from randomization to death of any cause. The same analyses as for DOR will be performed for OS.

The assumptions for the statistical method considered will be assessed by using standard techniques. In the case the assumptions are not met, the necessary adjustments for methods specified above will be introduced and reported.

*Analysis of other end points.* Cost modeling and validation will apply a model specifically developed for CRC by Investigator at Health Services Research Center, Akershus University Hospital [Joranger et al., 2015].

For *exploratory analyses*, appropriate statistical methods will be applied to analyze the various outcome measures.

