5.5 Duration of therapy

The **control arm** will consist of intermittent treatment with the Nordic FLOX regimen in terms of 8 cycles (16 weeks) before a break until disease progression, when therapy is reintroduced and administered for another 8 cycles before a new break. This go-and-stop schedule, which is chosen because continuous FLOX treatment commonly causes unacceptable toxicity in the palliative setting, will be continued until progressive disease on ongoing therapy (defining PFS in terms of failure of treatment strategy), unacceptable toxicity, withdrawal of consent, or death, whichever occurs first.

The estimated median PFS in the control arm is 9 months (*i.e.*, 39 weeks), as detailed in [Chapter 10](#). During this period, it is assumed that the ‘average’ patient will receive 1 full go-and-stop treatment sequence, consisting of 16 weeks of active therapy followed by 8 weeks of break until disease progression, before the second treatment period results in progressive disease after 16 weeks on ongoing therapy; hence, a PFS of 40 weeks. During the entire treatment, this patient will receive 2 sequences of active therapy, each containing 8 FLOX cycles.

The **experimental arm** will consist of repeat 2 cycles of the Nordic FLOX regimen followed by 2 cycles of nivolumab for a total of 8 individual cycles (16 weeks) before a break until disease progression, when therapy is reintroduced and administered for another total of 8 individual cycles before a new break. This go-and-stop schedule will be continued until progressive disease on ongoing therapy (defining PFS in terms of failure of treatment strategy), unacceptable toxicity, withdrawal of consent, or death, whichever occurs first.

[figure not shown]

Figure 4 – the experimental treatment arm.

The estimated median PFS in the experimental arm is 18 months (*i.e.*, 78 weeks), as detailed in [Chapter 10](#). During this period, it is assumed that the ‘average’ patient will receive 3 full go-and-stop treatment sequences, each consisting of 16 weeks of active therapy followed by 8 weeks of break until disease progression, before the fourth treatment period results in progressive disease after 8 weeks on ongoing therapy; hence, a PFS of 80 weeks. During the entire treatment, this patient will receive 4 sequences of active therapy, each containing 4 cycles each of FLOX and nivolumab.

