7.6.5 Frequency of tumor re-evaluation

Frequency of tumor re-evaluation will be every 8 weeks in both arms and during planned study treatment breaks. In the case of suspected clinical progression or iUPD according to iRECIST, the next evaluation may be preponed to after 4 weeks.

Evaluation will be with routine CT of the thoracic/abdominal/pelvic cavities, preferably with contrast in the case of adequate renal function.

If brain or bone metastasis is suspected, supplemental MR evaluations may be undertaken. However, bone scans only need to be repeated when CR is identified in target disease or when progression in bone is suspected.

All target and non-target sites are assessed at each evaluation.

After discontinuation of protocol treatment, patients who have not progressed will still be re-evaluated every 8 weeks until end-of-study, as per protocol.

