### **1.2. Objectives**

*Primary objective:* To determine progression-free survival (PFS), in terms of failure of treatment strategy, on sequential treatment with the Nordic FLOX regimen and nivolumab compared with the standard-of-care Nordic FLOX regimen in previously untreated metastatic MSS-CRC.

*Secondary objectives:*

- i) To determine safety and tolerability of sequential treatment with the Nordic FLOX regimen and nivolumab compared with the standard-of-care Nordic FLOX regimen.
- ii) To determine objective response rate (ORR), duration of response (DOR), secondary surgical curative resection rate (SSCRR), and overall survival (OS).
- iii) To monitor and compare quality-of-life (QoL) alterations during therapy courses.

*Tertiary objective:* To compare costs for the resource use (in diagnostic work-up, treatment, and any adverse events) for the sequential therapy with that of the standard-of-care, applying a model specifically developed for CRC.

*Exploratory objectives:*

- i) To develop circulating biomarkers of cytotoxic T lymphocyte activity.
- ii) To develop circulating biomarkers of tumor response.
- iii) To develop circulating biomarkers of immunogenic cell death.
- iv) To develop functional MR imaging biomarkers.
- v) To develop histologic and molecular tumor biomarkers.

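### The SAP and protocol calculate PFS to first recorded progression with no on-therapy condition, whereas the primary objective and protocol 5.5 define the event as progression on ongoing therapy

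*SAP*

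**What the plan says.** **Objective.** SAP 1.2 sets the primary objective: "To determine progression-free survival (PFS), in terms of failure of treatment strategy". The protocol synopsis and chapter 2 say the same.

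**Design.** Protocol 5.5 gives both arms 16 weeks of active therapy followed by a break. For the control arm the block is given "before a break until disease progression, when therapy is reintroduced and administered for another 8 cycles before a new break", and the experimental arm follows the same pattern with alternating cycles. In both arms the schedule runs until "progressive disease on ongoing therapy (defining PFS in terms of failure of treatment strategy"), unacceptable toxicity, withdrawal of consent or death. Footnote 1 of the flow chart agrees: the sequence is repeated after a break that ends in progression, until there is progression on therapy.

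**Planning figures.** Protocol 5.5 illustrates the 9- and 18-month medians with one average patient per arm. The control patient completes one full sequence "before the second treatment period results in progressive disease after 16 weeks on ongoing therapy; hence, a PFS of 40 weeks". The experimental patient completes three "before the fourth treatment period results in progressive disease after 8 weeks on ongoing therapy; hence, a PFS of 80 weeks". Protocol chapter 3 and SAP 2.1 list 9 and 18 months as the expected duration until strategy failure.

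**Analysis rule.** SAP 5.2, protocol 7.6.1 and protocol 10.4.1 all state that "PFS will be calculated from the day of randomization to first recorded disease progression" by RECIST v1.1, or iRECIST when applicable, or death. None requires the patient to be on therapy at progression, and none says how a progression in a break is handled.

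**The concern.** The trial expects progression in a break and responds to it by restarting the assigned treatment. Under protocol 5.5 that progression is a step within the strategy and not its failure. Scans continue every 8 weeks during breaks (protocol 7.6.2.1, 7.6.5 and the flow chart), so these progressions will be recorded. A rule that takes the first recorded progression will count them.

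The primary test would then stop at the first break progression for patients who get that far, and would discard whatever later sequences show. It would compare time to first progression, which is a legitimate endpoint but not the one in the objective. It is also not the one that protocol 5.5 ties to the planning medians. Two statisticians working in good faith from these documents could build different primary datasets.

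The ambiguity reaches monitoring too. Protocol 10.4.2 has the committee count PFS times well below 9 months, and protocol 9.4 links possible early termination to the ratio of PFS events between arms. Both depend on which event is meant.

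**Working it through.** **1. Does another section supply the missing condition?** No.
- SAP 5.1 gives the scan interval and response criteria only.
- Protocol 7.6.6 dates progression by RECIST PD in the control arm and iCPD in the experimental arm, without reference to therapy status.
- The censoring sentence in SAP 5.2 uses unqualified progression.
- SAP 5.4 plans no further analyses, so strategy failure would not be tested elsewhere.

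**2. Reproducing the stated sample size (SAP 2.3).** Inputs: HR 0.5, 80% power, 5% level (taken as two-sided), log-rank test, 10% censoring.
- Freedman events: ((1 + 0.5)/(1 − 0.5))² × (1.960 + 0.842)² = 9 × 7.85 = 70.6, so 71 events.
- Patients: 71/0.9 = 78.9, so 40 per arm, as stated.
- Inflation for 5% non-MSS cases and a further 20%: 80 × 1.05 × 1.20 = 100.8, against a stated 100.

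The arithmetic is sound for HR 0.5. The question is which event that HR describes.

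**3. The two events in protocol 5.5's average patients.**

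| | First recorded progression | Progression on ongoing therapy |
|---|---|---|
| Control | 16 + 8 = week 24 | 24 + 16 = week 40 |
| Experimental | 16 + 8 = week 24 | 3 × 24 + 8 = week 80 |

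Protocol 5.5 equates 9 months with 39 weeks and 18 months with 78 weeks. Those correspond to the right-hand column. Week 24 is 24/(52/12) = 5.5 months. In this illustration the written rule moves the event 16 weeks earlier in control and 56 weeks earlier in the experimental arm.

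**4. Power under the written rule.** The documents give no HR for first progression, so the HRs below are assumptions. Events: 100 × 0.95 × 0.9 = 85.5, taken as 86. Power = Φ(√(86/4) × |ln HR| − 1.96), plus the small opposite tail, with √(86/4) = 4.637.

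| Assumed HR, first progression | Power |
|---|---|
| 1.0 | 5% |
| 0.9 | 8% |
| 0.8 | 18% |
| 0.7 | 38% |
| 0.6 | 66% |
| 0.5 | 90% |

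If 24 weeks were the control median for first progression and times were exponential, HR 0.5 would need an experimental median of 24/0.5 = 48 weeks.

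**5. Would adding an on-therapy condition be enough?** Not alone. Protocol 7.6.3 measures PD from the smallest sum recorded on study. A patient whose target lesions progressed in the break, and who is merely stable after the restart, can still exceed that threshold at the next scan. The break progression would then be scored as failure at about 24 + 8 = week 32, not at week 40 or 80.

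**The case against.** The strongest reply is that the event is already defined. Protocol 5.5 states it for both arms, the objective repeats it, and a reader could take the analysis sentence as shorthand. Some protocol text supports this. Sections 5.7.2.4 and 7.7.4 require discontinuation on confirmed progression, which cannot include break progressions because those restart therapy. But usage is mixed: protocol 5.5 and the flow chart also use plain disease progression for the break event. So it does not follow that an analyst would inevitably score break progressions. It does follow that the sentence governing the calculation says first recorded, and that nothing in the SAP qualifies it.

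Several stronger conclusions are tempting and are not supported:

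- *The HR would be about 1 and the power about 5%.* A reader might infer this from 24 against 24 weeks. Those are two single illustrative timelines with an assumed 8-week break in each, not distributions. A log-rank HR cannot be read from them.
- *No benefit could appear at first progression.* Protocol 4.6 anticipates durable effects, and 5.5 cites disease control maintained off treatment in another cancer. Either could lengthen the first break.
- *The sample size was calculated on strategy-failure medians.* SAP 2.3 takes 9 months from publications and doubles it. The documents do not show how those publications defined PFS. The link to strategy failure comes from protocol chapter 3 and 5.5 and from SAP 2.1. Because 5.5 fits a schedule to the chapter 10 medians, the 40- and 80-week match is not independent confirmation.
- *Every patient is affected.* Patients who progress or die during the first active sequence are scored the same under both rules.

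**Conclusion.** The point stands: the operational definition of the primary endpoint conflicts with the primary objective and with protocol 5.5, and it needs correcting. Taken literally, the three calculation passages test time to first progression, while the objective concerns failure of strategy. Patients who reach a break and progress there are scored differently under the two rules.

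The size of the effect on the result is unknown. The only document-based indication is the illustration in protocol 5.5: week 24 in both arms for first progression, against weeks 40 and 80 for strategy failure. The 5% to 90% power range rests on assumed hazard ratios, 86 events, a two-sided 5% test and the Schoenfeld approximation. It shows how far the stated power depends on an effect that the plan never specifies for this event. It is not a forecast.

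**What to change.** In SAP 5.1 and 5.2 and protocol 7.6.1 and 10.4.1, use one definition: time from randomisation to first progression on ongoing study therapy (strategy failure as in protocol 5.5) or death. Then state:

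1. Progression in a planned break followed by reintroduction of study therapy is not an event.
2. How progression is counted when study therapy is not reintroduced, and on what date.
3. Which reference sum applies after a restart, and how a new lesion first seen in the break is treated, so that the break progression is not counted again at the first on-therapy scan.
4. Time to first recorded progression, or death, is reported as a supporting analysis.

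If the sponsor does intend first recorded progression as primary, the objective, protocol 5.5 and the basis for the 9- and 18-month assumptions must change instead.

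Two matters should be settled separately: the choice between RECIST and iRECIST in each arm, and the differing assessment schedules after discontinuation (protocol 7.6.5, 7.7.3.2 and the flow chart).

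The cost is mainly wording. Scan dates, treatment dates and target-lesion measurements are already collected; item 3 may need some re-derivation from the recorded measurements. Protocol 10.4.1 permits changes to the statistical plan until database lock. In an open-label trial this one should be made well before then, without reference to outcome data by arm.

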5.7.2.4 Continuing nivolumab with suspected progression

Accumulating evidence indicates that a minority of subjects treated with immune-modulating therapy may derive clinical benefit despite initial evidence of disease progression, such as inflammatory reaction simulating progression, so-called pseudo-progression. Subjects may, at the discretion of Clinical Investigator, continue study treatment in the setting of suspected progression until progression is confirmed, in accordance with the evaluation algorithm detailed for RECIST/iRECIST (*c.f.*, [Paragraph 7.6](#)). If Clinical Investigator believes that the subject continues to derive clinical benefit by continuing treatment, the subject should continue monitoring/assessments according the same schedule as patients without tumor progression, with more frequent radiologic assessment if clinically indicated (see below).

Subjects may continue study treatment beyond initial (suspected) progression only if they meet the following criteria:

- Subject is in stable performance status (ECOG 0–1) and tolerates study treatment.
- Treatment will not delay intervention to prevent imminent complications.
- There is overall clinical benefit as judged by Clinical Investigator.

Radiographic assessment should be repeated after suspected progression as clinically required in order to determine whether there has been a decrease in the tumor size or continued progression. Potential for clinical benefit should be balanced by clinical judgment as to whether the subject is clinically deteriorating and unlikely to receive benefit from continued study treatment. Study treatment will be permanently discontinued upon confirmation of progression.

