7.3.5 Subsequent anti-cancer therapy status

Clinical Investigator or a qualified designee will review all new anti-neoplastic therapy initiated after the last dose of trial treatment. If a subject initiates a new anti-cancer therapy within 30 days after the last dose of trial treatment, the 30 day safety follow-up visit must occur before the first dose of the new therapy. Once new anti-cancer therapy has been initiated the subject will move into survival follow-up.

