7.6.6. Date of progression

This is defined as the first day when RECIST (v1.1) PD is observed in the control arm and after iRECIST iCPD is observed in the experimental arm.

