## 2.3. Sample size

Calculation of sample size was performed for PFS – the primary end point – and based on PFS data from recent publications. A median PFS of 9 months was assumed for the standard-of-care (control arm) [Cartwright, 2012; Tveit et al., 2012; Cremolini et al., 2015]. Regarding the therapy concept of ICB, there is no PFS data published as yet for the setting of interest. In the study of patients with treatment-refractory metastatic CRC, median PFS was not reached in the cohort with mismatch repair-deficient disease at the time of reporting [Le et al., 2015]. In the study of previously untreated patients with advanced non-small cell lung cancer, which is a tumor entity with considerably poorer prognosis than advanced CRC, patients with PD-L1-positive tumors that were randomized to ICB showed median PFS of 10.3 months compared to 6.0 months for standard chemotherapy [Reck et al., 2016].

Extrapolating to the setting of interest, with a median PFS of 9 months for standard-of-care, a median PFS twice as long (18 months) was entered for the sequential therapy. Assuming the exponential distribution of survival functions, the median PFS estimates were converted to hazard ratio (HR) of 0.5. Allowing for 10% censoring rate of subjects, the required sample size was estimated to be 40 patients in each arm to be able to show that HR of 0.5, implying the risk of a PFS event in the experimental group is 50% lower than in the control group, is significantly different from 1 with the power of 80% at significance level of 5%, given that log-rank test will be used.

However, it was necessary with several adjustments of the above calculations to maintain sufficient power. First, the sample size was adjusted to enable removal of a maximum of 5% enrolled cases with non-MSS tumor before data analysis. Next, keeping in mind the condition of patients, it is not unlikely that some will be lost from the study before a valid PFS event has been reached. Also, a number of analyses stratified by primary tumor sidedness and (K)RAS/BRAF mutation status will be performed. Hence, to enable high enough power in the statistical analysis, the sample size was increased by an additional 20%. After

incorporating the adjustments, the final sample size was estimated to be 100 patients, 50 in each arm, with 1:1 randomization.

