# **3. Statistical Principals**

## **3.1. Confidence intervals and P values**

Level of statistical significance is set to 5% in all analyses. Whenever relevant, 95% confidence intervals (CIs) will be reported. No adjustment for multiple testing will be introduced. However, all performed statistical analyses will be reported in the publications leading to transparency and enabling reader to judge the validity of the reported p-values.

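### Protocol 7.6.6 gives no event date to an experimental-arm iUPD that is never confirmed or refuted: it counts only at death or is censored, while the same scan in the control arm is an event at once

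*SAP*

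**What the plan says.** - **Event and censoring.** SAP 5.2 (and Protocol 7.6.1 and 10.4.1) runs PFS from randomization to progression by RECIST 1.1, or iRECIST where that applies, or death. The only censoring rule is "Patients who have not had disease progression at the time of final analysis will be censored", at the last date known alive without progression.
- **Date of progression.** Protocol 7.6.6 uses the first RECIST 1.1 PD in the control arm, but takes progression "after iRECIST iCPD is observed in the experimental arm".
- **Confirmation.** Protocol 7.6.4 applies iRECIST to the experimental arm. iCPD requires further growth or new lesions at the next assessment, 4–8 weeks after iUPD; unchanged disease stays iUPD.
- **Treatment after iUPD.** Protocol 5.7.2.4: "Subjects may continue study treatment beyond initial (suspected) progression only if they meet the following criteria". These concern performance status, tolerance, imminent complications and judged benefit.
- **After new therapy.** Protocol 7.3.5: "Once new anti-cancer therapy has been initiated the subject will move into survival follow-up". Sections 7.7.3.2 and 7.7.4 also end disease follow-up at that point.
- **After stopping alone.** Protocol 7.6.5 keeps patients without progression on 8-weekly imaging. Section 7.7.3.3, however, moves a patient to survival follow-up on stopping, and the flow chart marks no CT after the visit at treatment discontinuation.

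**The concern.** Under 7.6.6 a suspicious scan is an event in one arm and a provisional finding in the other. The provisional finding becomes an event only if the patient is assessed again, and the protocol's own pathway takes some patients away before that happens. No sentence says what the provisional finding is then worth.

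The primary endpoint would then lose or postpone events in the experimental arm only, which lowers the hazard ratio. The loss would also be related to prognosis, because patients who do not meet the criteria for continuing are more likely to leave before the confirming scan. The SAP would not reveal the problem: section 5.3 plans no handling of missing data unless it proves substantial, and section 5.4 plans no further analyses, so there is no comparison using RECIST 1.1 in both arms.

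**Working it through.** **1. The plan's own figure.** Inputs from SAP 2.3: "a median PFS of 9 months for standard-of-care, a median PFS twice as long (18 months) was entered for the sequential therapy"; "with the power of 80% at significance level of 5%, given that log-rank test will be used"; "Allowing for 10% censoring rate of subjects, the required sample size was estimated to be 40 patients in each arm". Sidedness is not stated.

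- Freedman, two-sided: (1.960 + 0.842)² × [(1 + 0.5)/(1 − 0.5)]² = 7.85 × 9 = 70.6, so 71 events. 71/0.90 = 78.9, so 79 patients, or 40 per arm. This reproduces the plan.
- Schoenfeld: 4 × 7.85/(ln 0.5)² = 65.3, so 66 events, 74 patients, 37 per arm. This does not.
- Final size: 80 × 1.05 × 1.20 = 100.8, close to the stated 100.

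The test is therefore taken as two-sided 5%, so a false win for the experimental arm has a nominal rate of 2.5%.

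**2. One scan, two arms.** Take a scan meeting RECIST 1.1 progression on therapy, followed by new anti-cancer therapy before any further scan.

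| | Control | Experimental, under 7.6.6 |
|---|---|---|
| Status at the scan | PD | iUPD |
| PFS event date | that scan | none |
| Later death | already counted | event, at death |
| Alive at cut-off, or lost | already counted | censored |

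**3. Events at risk.** Assume no treatment effect, both medians 9 months, uniform accrual over 12 months, and a cut at month 30 (1 March 2018 to 1 September 2020). With λ = ln 2/9 = 0.0770, the probability of an event is 1 − (e^(−18λ) − e^(−30λ))/(12λ) = 1 − (0.250 − 0.099)/0.924 = 0.837. That is 41.8 events per arm. If a share f of experimental-arm progressions is never confirmed, f = 10%, 20% and 30% mean about 4, 8 and 13 patients. The documents give no value for f.

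**4. Closed form, if those patients are censored at iUPD at random.** The observed experimental hazard falls to (1 − f)λ, so the apparent HR is 1 − f. With d events in total, the mean of z is ln(1 − f) × √d/2, and the false-win probability is Φ(−1.96 − mean z).

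- f = 10%, d = 79.6: mean z = −0.105 × 4.46 = −0.47; Φ(−1.49) = 6.8%.
- f = 20%, d = 75.4: mean z = −0.223 × 4.34 = −0.97; Φ(−0.99) = 16.1%.
- f = 30%, d = 71.2: mean z = −0.357 × 4.22 = −1.50; Φ(−0.46) = 32.4%.

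**5. Simulation.** 50 per arm, null true, accrual and cut-off as in step 3, log-rank z < −1.96. Entries are apparent HR / false wins for the experimental arm.

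| Handling of unconfirmed iUPD | f = 10% | f = 20% | f = 30% |
|---|---|---|---|
| Censored at iUPD | 0.90 / 6.4% | 0.80 / 15.6% | 0.70 / 32.0% |
| Censored one scan earlier | 0.91 / 5.9% | 0.82 / 13.3% | 0.72 / 25.8% |
| Event at death, median 12 months later | 0.89 / 8.0% | 0.79 / 17.4% | 0.71 / 33.6% |
| Event at death, median 3 months later | 0.96 / 3.9% | 0.92 / 5.5% | 0.89 / 7.0% |

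The first three rows use 5,000 replicates; the last uses 3,000, with progression seen on an 8-week scan grid. Repeats gave about 6%, 14% and 29% when censored, 7%, 18% and 31% at death with a 12-month median, and 4–6% with a 3-month median. The spread at f = 30% reflects the censoring date, the scan grid and simulation error. Making early progressors twice as likely to be lost changed little (6.8% and 13.1% at f = 10% and 20%, censored).

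Under the design HR of 0.5, censoring 10%, 20% or 30% gives an apparent HR of 0.45, 0.40 or 0.35.

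**6. With a rule.** If an unresolved iUPD counts on its own date, nothing is lost: HR 1.00 with 2.2% false wins under the null, and HR 0.50 with 83% power under the design effect.

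**The case against.** **Death is a PFS event, and nothing censors at new therapy.** This stands. A reader might infer that a patient with an unconfirmed iUPD never becomes an event; the documents do not support that. A later death counts, and the event is lost only if the patient is alive at cut-off or lost to follow-up. Counting at death does not remove the bias, though: with a 12-month median it is about as large as with censoring.

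**Stopping treatment is not the same as leaving imaging.** This stands in part. A reader might infer that everyone who stops after iUPD misses the confirming scan. Protocol 7.6.5 keeps patients without progression on 8-weekly imaging and lets the scan after iUPD come at 4 weeks, and 7.7.4 continues disease follow-up. But 7.7.3.3 and the flow chart conflict with this, and 7.6.5 does not say whether an iUPD patient counts as not progressed. New therapy before confirmation is the clear path.

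**RECIST 1.1 is the primary method (Protocol 7.6.1).** If that governed PFS, the first PD would count in both arms and the problem would vanish. Yet the PFS sentence in 7.6.1 itself admits iRECIST, as does SAP 5.2, and 7.6.6 is the only section that defines the date. The passages contradict each other.

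**Exposure may be limited.** Protocol 5.7.2.4 and 7.7.4 tie permanent discontinuation to confirmed progression, and under 5.5 progression during a break leads to reintroduced therapy with scans continuing. So the unconfirmed share could be small; the 10–30% range is an assumption.

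**Fast deterioration means early death.** If the patients lost are the sickest, their events arrive soon and the bias shrinks to the 3-month row. This stands as a limit on size.

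**Conclusion.** The gap is real and one-directional. With 7.6.6 governing, an experimental-arm iUPD that is never re-assessed is delayed to death or censored, while the same finding in the control arm is an event at once. This favours the experimental arm on the primary endpoint.

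The direction follows from the text; the size does not. It depends on the unconfirmed share (assumed 10–30%), on what the analyst does with these patients, and on their survival after iUPD (assumed medians of 12 or 3 months). Across those assumptions the false-win rate runs from about 4%, modest inflation over 2.5%, to about 30%. The figures exclude any effect of dating confirmed progressions at the later scan, which is a separate matter. The planned sample size is unaffected.

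**What to change.** 1. Reconcile Protocol 7.6.1, 7.6.6 and SAP 5.2 so that one statement says which criterion defines the PFS event in each arm.
2. If iCPD is kept for the experimental arm, add to 7.6.6 and SAP 5.2: an iUPD not followed by a confirming or refuting assessment, because treatment stopped, new anti-cancer therapy began, the patient died or no scan was done, counts as progression on the iUPD date. Only an iUPD followed by an assessed iSD, iPR or iCR is set aside.
3. Prespecify a sensitivity analysis of PFS using the first RECIST 1.1 PD in both arms.

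No new data are needed: under Protocol 7.6.1 the study radiologist reads RECIST 1.1 first and turns to iRECIST only after RECIST progression, so the dates should exist. Protocol 10.4.1 permits changes to the plan until database lock. The cost is a few sentences, a little more analysis, and slightly less favourable PFS in the experimental arm.
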